laparotomy would be recommended. However, the decision regarding subsequent laparotomy is the responsibility of the treating physicians and not dictated by this study. Factors to be considered in performing a subsequent laparotomy will include the usual scenarios in current practice. Reasons surgeons use to perform a laparotomy after initial drainage include: continued deterioration despite adequate drainage (e.g. increased pressor requirement, worsened coagulation profile, increasing ventilator support, decreasing urine output, increasing or persistent pneumoperitoneum, worsened abdominal wall discoloration or abdominal mass, or others). Alternatively, some surgeons proceed with a subsequent laparotomy if the patient improves after initial drainage, arguing that with improvement the risk for laparotomy has fallen to an acceptable level. This will also be allowed and recorded in this study. The reasons that study patients undergo subsequent laparotomy will be recorded. Other than randomizing the original treatment option, the trial will attempt to allow standard current practice to facilitate enrollment and to increase generalizability.

Initial laparotomy will be performed under general anesthesia in the NICU or operating room. Standard procedures will be used, including inspection of the bowel with resection of diseased areas, creation of stoma(s), and other procedures felt to be indicated by the surgeon. Intraoperative data recorded by the surgeon will include complications, intestinal length removed and remaining, presence of ileocecal valve, etc. As appropriate in a management trial,²¹ use of surgical and medical cointerventions will be determined by the attending pediatric surgeon and neonatologist. Patients undergoing initial laparotomy may also undergo subsequent laparotomy as indicated.

Issues Regarding Subsequent Laparotomy after Initial Surgical Treatment (either drain or laparotomy).

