An important issue (for this trial and for neurodevelopmental assessment of premature infants in general) is the potential difference in sensitivities of the Bayley II and III products in defining NDI. Some authors have reported recently that the Bayley III likely underestimates NDI, compared to the Bayley II.³¹ Because of these issues, for this trial a Bayley III score of <85 will be one of the conditions defining NDI (in addition to those above).

Blinding and Reliability. Blinded collection of predischarge data would not be reasonably feasible for our research nurses. Follow-up personnel who are not told the treatment group will assess all follow-up findings. Because patients in each treatment group are likely to require laparotomy after the initial surgical procedure, it will be difficult to predict treatment group assignment at 18-22 months by simply examining the child, as infants in both groups may have undergone multiple abdominal procedures. The final assessment of impairment will be reviewed by three subcommittee members without knowledge of treatment group who will adjudicate the outcome of any infants whose outcome is uncertain (as was done Hypothermia trial).

Statistical Analyses. The primary analysis will assess the effect of treatment on death or NDI at 18-22 months corrected age. This analysis will be performed using standard statistical analyses often used in multicenter trials: logistic regression equations in which the predictor variables include treatment group and the stratifying variables (in this trial, center, and risk stratification formula). The analyses will include an assessment of whether there is an interaction between treatment (laparotomy or drainage) and disease (NEC or IP). Bayesian analyses^{11, 15} of the primary outcome will also be performed because statistical power will be limited to identify treatment effects that are clinically important but smaller than hypothesized and because Bayesian analyses can be used to estimate the (posterior) probability that laparotomy reduces death or NDI at 18-22 months.

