The top table of the output just lists the boundary values and the nominal p-values for each boundary value on the scale of a z statistic for sample sizes of 30, 60, 90, 120, 180, 240, and 300 infants. The “Upper boundary” lists the conditional probability of crossing the upper boundary given no previous boundary crossings (upper or lower) under the null hypothesis of no difference. The “Lower boundary” lists the conditional probability of crossing the lower boundary given no previous boundary crossings (upper or lower) under the null hypothesis of no difference. Within each list, the value given in the “Total” column is the overall error attributed to that boundary. Based on these calculations, a boundary set of z statistics equal to $\{-2.516, 2.516\}$ will produce lower and upper Pocock boundaries for 6 interim analyses and 1 final analysis of mortality.

For this interim assessment of mortality, robust Poisson regression of death at time of Network status will be used as the outcome variable. The robust Poisson regression model will have at least treatment and baseline risk as covariates. In addition, if possible, the robust Poisson regression model will include center as a fixed covariate. This robust Poisson regression model will be called the primary interim mortality model. For the robust Poisson regression, the outcome for the i^{th} infant will be:

$$y_i = \begin{cases} 0 & \text{for survival at Network Status} \\ 1 & \text{for death at Network Status} \end{cases}$$

The covariates will have the form:

$$s_i = \begin{cases} 0 & \text{initial surgery was drain} \\ 1 & \text{initial surgery was laparotomy} \end{cases}$$

$$r_i = \begin{cases} 0 & \text{low baseline risk for death or NDI} \\ 1 & \text{high baseline risk for death or NDI} \end{cases}$$

The model will have the form:

$$y_i | (s_i, r_i, c_i) \sim \text{Poisson}[\lambda(s_i, r_i, c_i)] \text{ where}$$

$$\log[\lambda] = \alpha + \beta \cdot s_i + \gamma \cdot r_i + \nu_c \cdot c_i \text{ and } c_i \text{ represents the site for the } i^{\text{th}} \text{ infant among } C \text{ total sites.}$$

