maxn.IPlan=300)
OF.update$upper$bound
```

where L equals the total number of completed and still to complete looks such as 4, and $vec.L$ contains a modified list of sample sizes at the exact and still to be completed looks such as $c(81,150,225,300)$. Note that the spending function is now “sfLDOF”, which specifies that the boundaries will be recalculated given new sample size points based on the Lan-DeMets approximation of O’Brien-Fleming boundaries.

At the time of each interim analysis, the boundaries for the current and future interim analyses will be updated using `gsDesign()` as described above. A robust Poisson regression model will be used to analyze the primary outcome of death or NDI at 18-22 months. For the robust Poisson regression, the outcome for the i^{th} infant will be:

$$y_i = \begin{cases} 0 & \text{for survival without NDI} \\ 1 & \text{for death or survival with NDI} \end{cases}$$

The covariates will have the form:

$$s_i = \begin{cases} 0 & \text{initial surgery was drain} \\ 1 & \text{initial surgery was laparotomy} \end{cases}$$

$$r_i = \begin{cases} 0 & \text{low baseline risk for death or NDI} \\ 1 & \text{high baseline risk for death or NDI} \end{cases}$$

The model will have the form:

$$y_i | (s_i, r_i, c_i) \sim \text{Poisson}[\lambda(s_i, r_i, c_i)], \text{ where } \log[\lambda] = \alpha + \vartheta \cdot s_i + \gamma \cdot r_i + \nu_c \cdot c_i \text{ and } c_i \text{ represents the site for the } i^{\text{th}} \text{ infant among } C \text{ total sites.}$$

Similar to the safety interim analysis, the test statistic produced for the treatment effect will be a z-statistic. This z-statistic will be compared to the appropriate boundary pair calculated from the updating call to `gsDesign()`. The actual robust regression modeling at each interim analysis will be completed in SAS, and a figure summarizing the interim

analysis results will be constructed in Excel. Prior interim analysis results will be represented in the figure as well.

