The primary analysis of randomized cohort data will assess the effect of treatment on death or NDI at 18-22 months corrected age, death, and other clinical outcomes as defined in Study Endpoint section above (pages 8-10) and listed on pages 13 and 14. This analysis will be performed using a robust Poisson regression model identical to the model defined on page 17 and 18. If possible center will also be included in the model as a fixed or random effect. The default will be a fixed effect, but a random effect may be used if model convergence issues results from using a fixed effect. The outcome variable will assign one to the event of death or NDI at 18-22 months corrected age and zero otherwise. The treatment variable will assign one to laparotomy and zero to drainage. It follows that relative risks less than one (or less than zero on the log scale) will favor Laparotomy.

Like the efficacy interim analysis, the final test statistic produced for the treatment effect will be a z-statistic. This z-statistic will be compared to the appropriate boundary pair calculated from the updating call to `gsDesign()` as described in the efficacy interim analysis section. As with the interim efficacy analyses, the actual robust regression modeling at each interim analysis will be completed in SAS, and a figure summarizing the final analysis results will be constructed in Excel. This figure will contain information from all prior interim efficacy analysis results.

In addition to the above formal adjusted analyses, simple unadjusted treatment comparisons of randomized data will be completed, and 95% confidence intervals of differences in proportions will be constructed. The formatting of these tabulations will be determined as the corresponding papers develop.

Secondary Analysis of Primary Outcome Using Randomized Cohort Data

The analyses will include an assessment of whether there is an interaction between treatment (laparotomy or drainage) and disease (NEC or IP). This assessment will use a robust Poisson regression model with will include treatment (laparotomy or drainage), preoperative diagnosis (NEC or IP), and the treatment by preoperative diagnosis interaction. If the Wald test for the interaction term has a p-value less than 0.05, then the conclusion will be the study has produced evidence of an interaction between treatment and pre-operative diagnosis with respect to the primary outcome. If such

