Given the robust Poisson regression estimates of $\log(\text{RR})$ are approximately normal, Bayesian analysis of the primary outcome will also use the normal approximation approach of Spiegelhalter, Abrams, and Myles. Namely, the marginal likelihood for the treatment effect will be approximated by a normal distribution with mean equal to the robust Poisson regression estimated log relative risk and standard deviation equal to the sandwich estimate of the log relative risk standard error. The robust Poisson regression model used in this analysis will be the same as the model defined on page 17 and 18. The model will also adjust for center by including center as a fixed effect, if possible.

In addition to assuming the marginal likelihood of the treatment effect is approximated by a normal distribution, normal priors will be used as well. As a consequent, the posterior will be a normal distribution with mean equal to a weighted average of the prior mean and the maximum likelihood estimate of the log relative risk calculated from the data. The variance of the posterior will be the inverse of the sum of the precisions (1/variance).

Prior:
$$p(\theta) = N(\theta | \mu, \sigma^2), \text{ where } \theta = \log(\text{RR})$$

Likelihood:
$$p(\text{data} | \theta) = N(\hat{\beta}_{\text{trt}}, se_{\text{sand.}}^2)$$

$$\text{Posterior: } p(\theta|data) = N \left(\frac{\frac{\mu}{\sigma^2} + \frac{\hat{\beta}_{irt}}{se_{sand.}^2}}{\frac{1}{\sigma^2} + \frac{1}{se_{sand.}^2}}, \frac{1}{\frac{1}{\sigma^2} + \frac{1}{se_{sand.}^2}} \right)$$

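### The SAP defines the treatment covariate by what the initial surgery was, and neither document says that randomised infants are analysed in their assigned arm

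*SAP*

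**What the plan says.** The SAP writes out the covariate s_i three times: in Interim Mortality Assessment, in Interim Efficiency Assessment and in Bayesian Analysis of Primary Outcome using Randomized Cohort Data. Each time s_i is 0 if the "initial surgery was drain" and 1 if the "initial surgery was laparotomy".

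Other sections inherit this definition:

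- The interaction model under Interim Mortality Assessment uses the same s_i.
- Primary Analysis of Randomized Cohort Data says that the analysis is "performed using a robust Poisson regression model identical to the model defined on page 17 and 18". It adds: "The treatment variable will assign one to laparotomy and zero to drainage". It does not say whether that means assigned or performed.
- In Statistical Appendix A the model "will be the same as the model defined on page 17 and 18".

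The page reference is not visible in the text supplied. The death-or-NDI model sits in Interim Efficiency Assessment, and the mortality model defines s_i in the same words, so the definition carried over is the same in either case.

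The protocol uses different language. Under Statistical Analyses, "the predictor variables include treatment group and the stratifying variables". Under Blinding and Reliability it speaks of whether an examiner could "predict treatment group assignment at 18-22 months". Under Treatment it describes what the trial fixes with the words "Other than randomizing the original treatment option".

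**The concern.** The only explicit definition of the covariate behind the primary z-test describes an operation that took place. Restricting the analysis to the randomised cohort fixes which infants are analysed, not how each is classified. Neither document states an intention-to-treat or as-randomised principle. Neither gives a rule for a randomised infant whose first procedure differs from the assignment, or who has none.

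A programmer who follows the written definition would code by surgery performed. If first-procedure departures depend on prognosis, that coding gives up the protection of randomisation and biases the relative risk, in a direction set by who switches. On the literal reading only, an infant who was never operated on would have no covariate value and would drop out.

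**Working it through.** **1. The plan's own figure.** Inputs from SAP, Interim Efficiency Assessment: risks 80% and 65%, 150 per arm, printed bounds 4.05, 2.86, 2.34 and 2.02. Exact two-sided Fisher power is 80.3%, against the stated 80%. An unadjusted log-RR test over the four looks gives 81.0%, against a stated 82% for the robust Poisson model. The design figures hold, so this point is not about arithmetic in the plan. They take assigned and received procedure to be the same.

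**2. Who is affected.** Laparotomy after an initial drain leaves s_i at 0 under either reading. Only an infant whose first procedure differs from the assignment, or who has none, is coded differently.

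**3. Hand calculation under no true effect.** Assumptions: overall risk 80%; 30% of infants are high-risk at 95%, so the rest have (0.80 − 0.30 × 0.95)/0.70 = 0.736. High-risk infants assigned laparotomy receive a drain instead, amounting to 10% of that arm (15 of 150).

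- Received laparotomy: (30 × 0.95 + 105 × 0.736)/135 = 0.783
- Received drain: (150 × 0.80 + 15 × 0.95)/165 = 0.814
- RR = 0.963
- SE of log RR = √[(0.217/0.783)/135 + (0.186/0.814)/165] = 0.0586
- Shift in z = −0.038/0.0586 = −0.65
- Type I error at 2.02 = Φ(−1.37) + Φ(−2.67) ≈ 8.9%

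The same steps at other rates:

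| Laparotomy-to-drain switching | RR as received | Type I error |
|---|---|---|
| 0% | 1.000 | 4.3% |
| 2% | 0.993 | 4.5% |
| 5% | 0.981 | 5.5% |
| 10% | 0.963 | 8.9% |

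By assigned arm the RR stays at 1.00 and the error at 4.3%.

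**4. Simulation with the SAP's model form.** Null trials of 300 with overall risk 72.5%. Severity is u ~ N(0,1) and the logit of risk is 1.235 + 1.2u. The baseline-risk stratum is 1 if u + N(0,1) > 0. Switching probability is x·exp(±1.5u − 1.125), capped at 1; nominal 2%, 5% and 10% give actual rates of 2.0%, 4.8% and 9.0%. The analysis is robust Poisson on s and stratum with a sandwich SE, centre omitted, and final bound 2.02. By assigned arm the error is 4.2%.

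| Coded by surgery performed | RR at 2.0 / 4.8 / 9.0% | Type I error |
|---|---|---|
| Unrelated to prognosis, both arms (2–10%) | – | 4.2–4.3% |
| Sicker infants, same rate in both arms | 1.00 | 4.2–4.3% |
| Sicker, laparotomy to drain only | 0.994 / 0.984 / 0.971 | 4.3 / 4.7 / 5.8% |
| Sicker, drain to laparotomy only | 1.006 / 1.016 / 1.029 | 4.3 / 4.6 / 5.7% |
| Sicker to drain and healthier to laparotomy | 0.980 / 0.954 / 0.918 | 5.1 / 9.2 / 20.8% |

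For one-way switching near 10%, steps 3 and 4 give 8.9% and 5.8%. The risk models differ, and step 4 adjusts for a stratum that absorbs part of the severity difference. Without that adjustment the step 4 figure is about 8%. The last row has equal rates in both arms and still inflates the error: what must match between arms is the kind of infant who switches as well as the number.

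**5. Infants with no operation (literal reading only).** Dropping 3 deaths from one arm at 72.5% risk: (108.75 − 3)/147 ÷ 0.725 = 0.992, or 1.008 if from the other arm. Dropping 8: (108.75 − 8)/142 ÷ 0.725 = 0.979, or 1.022.

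**The case against.** The strongest reply is that initial surgery is this trial's name for the randomised strategy. The title, the aims and the protocol's Treatment section all contrast initial drainage with initial laparotomy, and the protocol discusses later laparotomy at length. On that reading the word initial only keeps an infant who has a drain and then a laparotomy in the drain group, as the strategy comparison requires. This stands as a natural reading and is probably what was meant. It does not remove the ambiguity, because the same words describe the first operation received.

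Departures are also limited by design. Under the protocol's Consent, Enrollment, and Treatment Assignment, an infant is enrolled only if the surgeon agrees to randomise. The SAP places randomisation directly after the decision to operate. Eligibility requires that decision and full support, so infants with no operation should be few. The protocol's remark that some infants randomised to drainage would have had laparotomy by preference explains later laparotomy, which does not alter s_i. All this stands, and it keeps the expected effect small.

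The SAP also relies on an operations manual, case report forms and a data dictionary that were not supplied. The variable may be defined there.

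A reader might infer that the SAP plans an as-treated primary analysis. The documents do not support that: they speak of treatment group, assignment and arms, and the covariate wording alone does not show such a plan.

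**Conclusion.** The covariate's definition is ambiguous, and nothing in the protocol or SAP resolves it. With no departures the choice makes no difference. If departures occur and depend on prognosis, coding by surgery performed biases the relative risk. Type I error is unaffected only if departures are unrelated to prognosis, or if the same kinds of infants switch at the same rate in both arms.

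The size rests wholly on assumed departure rates and risk models. A few percent switching one way gives about 4–6% error. One-way switching near 10% of an arm gives about 6–9%. Opposite-direction switching gives more. The 20.8% figure should not be read as an expected error: it needs 9% of both arms to switch in opposite prognostic directions under a strong assumed selection slope. Nor is opposite-direction switching the only route to inflation, since the 8.9% arises from one-way switching.

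This is a minor point and an almost free improvement.

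**What to change.** In Interim Mortality Assessment, Interim Efficiency Assessment and the Bayesian analysis section, define s_i for the randomised cohort as the randomised assignment: 0 = assigned drain, 1 = assigned laparotomy. In Primary Analysis of Randomized Cohort Data, add one sentence that every randomised infant is analysed in the assigned arm whatever procedure, if any, was done first. The interaction model and Appendix A then inherit the definition. Report by arm the number whose first procedure differed from assignment and the number with none. Keep surgery performed as the exposure in the non-randomised cohort. A labelled as-treated sensitivity analysis is optional.

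The cost is wording only; no boundary, sample size or stated figure changes. If departures occur, assigned-arm coding loses some power. For true risks of 80% and 65%, 150 per arm and bound 2.02, power is Φ(|log RR|/SE − 2.02):

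- No departures: Φ(0.2076/0.0725 − 2.02) = 80.1%
- 2% switching in both arms, unrelated to prognosis (79.7% v 65.3%): 76.8%
- 5% switching in both arms, unrelated to prognosis (79.25% v 65.75%): 71.4%
- 5% from laparotomy to drain only (80% v 65.75%): 76.3%
- 5% from drain to laparotomy only (79.25% v 65%): 75.6%

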Stratification according to preoperative diagnosis. A unique design feature of this trial (as compared to the two prior RCTs in this patient population) is the stratification utilizing the presumed preoperative diagnosis (NEC or IP). We feel it is critical to make this distinction, to the best of our ability, to ensure maximal comparability of treatment groups and to have the ability to test for interactions between treatment and diagnosis. Based on the Network observational study and other data, the following patient characteristics support a preoperative diagnosis of NEC: presence of pneumatosis on KUB, older age at operation (mean age at operation from observational study = 27.8 days), and presence of portal vein air. A history of enteral feedings prior to disease occurrence has been suggested as supportive of a diagnosis of NEC in other publications. In the Network observational study, only 46% of patients with proven NEC (determined at laparotomy) had a pneumoperitoneum on preoperative imaging.³

The following characteristics support the diagnosis of IP: younger age at operation (mean age at operation in Network observational study = 7.4 days), absence of pneumatosis, and presence of pneumoperitoneum on preoperative KUB. Other characteristics that have been used to favor a diagnosis of IP include the radiographic finding of “gasless abdomen” and the physical exam finding of a “blue abdomen”. In the Network observational study, the last two characteristics were not statistically different between NEC and IP infants, but the findings supported using these as secondary determinants to help distinguish the two diagnoses.

In the Network observational study, the correlation of the preoperative diagnosis (NEC or IP) with intraoperative diagnosis in patients undergoing laparotomy was 95%. While recognizing that the distinction is not perfect preoperatively, we feel that this is a positive design feature and preoperative diagnosis of the pediatric surgeon will be recorded. Accuracy of this distinction will again be measured in those undergoing laparotomy.

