Baseline and Intraoperative Data. Baseline variables include: BW, GA, postnatal age, sex, and multiple measures of illness severity related to outcome in our prior study or other studies (blood pressure, vasopressor therapy, platelet count, pH, FiO₂, ventilator type, and settings), whether randomization was refused by the surgeon or parents, and if so, the stated reason. Preoperative and intraoperative observations will be recorded by the pediatric surgeon as in the observational study. Location of operative intervention (NICU or operating room) will be recorded.

Primary outcome variable, as defined above, is death or neurodevelopmental impairment at 18-22 months as assessed in the generic follow-up of ELBW infants in Network centers.

Secondary outcomes variables will include surgical complications, such as wound dehiscence, intestinal stricture or fistula, procedure-related liver hemorrhage; number of surgical procedures; sepsis episodes; duration of parenteral nutrition; parenteral nutrition associated cholestasis; length of hospital stay; rehospitalizations; and each component of the primary outcome.

Treatment. Initial drainage will involve placing a ¼ inch Penrose drain in the lower abdomen with local anesthesia and sedation. The drain will be fed into the peritoneal cavity toward the pelvis and sutured to the skin. There are differences in this technique that are used across the multiple sites (e.g. irrigation or not, right or left sided, etc...) and no specific techniques have been shown to correlate with either effectiveness of drainage or with the primary outcome of our study. Therefore, no formal guidelines regarding the drainage procedure are felt necessary. A standard dressing will be applied at the surgeon’s discretion.

Subsequent laparotomy will be allowed after initial drainage, since this trial is designed to test two treatment strategies (i.e. initial drain versus initial laparotomy), rather than a strict comparison of drain only vs. laparotomy only. The study protocol recommends reevaluation of the patient 12 – 24 hours after drain placement to consider the need for subsequent laparotomy. If the patient is improved, no subsequent

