4. patient is at a center able to perform both laparotomy and drainage.

Exclusion Criteria:

1. Major anomaly which influences likelihood of developing primary outcome or affects surgical treatment considerations;
2. congenital infection;
3. Prior laparotomy or peritoneal drain placement,

4. Prior NEC or IP,
5. Follow-up unlikely (e.g., mother incarcerated, or currently resides (or plans to move) far from any Network center.), and
6. Infant for whom full support is not provided (including surgical treatment).

Method of Treatment Assignment and Randomization

Infants enrolled into the randomized cohort will be randomized using a variable, permuted, block size scheme. Infants will be randomized by calling RTI International as soon as a decision to perform surgery is made (or via a computer randomization process). Randomized infants will be stratified according to two variables: center and according to the overall risk for death or NDI (higher / lower). The risk stratification formula was primarily developed in the prospective observational model and includes the following variables: birth-weight, gestational age, vasopressor requirement (yes / no), if infant is on high frequency (oscillating or jet) ventilation or not (any modality of conventional ventilation or no mechanical ventilation), pH, FiO₂, and preoperative diagnosis (NEC or IP). Treatment beyond the initial surgical management will be unaffected by the trial.

Treatment Masking

As this is a surgical trial, the surgeons will not be masked to randomized treatment. Outcome assessments at 18-22 months will be assessed by evaluators who are masked to the details of the operative intervention(s) that have been performed using standard Network assessments. The statistician is unmasked in this trial.

Sequence of Planned Analyses

Interim Analyses

Annual Data Safety Monitoring Committee (DSMC) meetings will be convened to monitor the progress of the trial and review the accruing safety and efficacy data. Starting one year after at least 11 sites have IRB clearance to start enrolling into the trial, safety data will be monitored. Once follow up data start becoming available (which should occur from the 2nd year onwards) interim efficacy data will also be presented to the DSMC. All figures, summaries, and listings created in the interim analyses and presented to the DSMC will be masked to treatment assignment, but interim analysis results will be unmasked at the DSMC's request.

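### The primary model adjusts only for a high/low split of a baseline risk formula; adding the numeric score is valid and would give a modest, possibly nil, gain in precision

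*SAP*

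**What the plan says.** The SAP, under Method of Treatment Assignment and Randomization, has infants "stratified according to two variables: center and according to the overall risk for death or NDI (higher / lower"). The formula behind the second factor takes seven inputs: birth weight, gestational age, vasopressor need, high-frequency ventilation, pH, FiO2 and preoperative diagnosis. Four of these (birth weight, gestational age, pH, FiO2) are continuous.

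Under Interim Efficiency Assessment, the robust Poisson model contains treatment, center and one binary risk covariate, coded 0 for "low baseline risk for death or NDI" and 1 for high. Primary Analysis of Randomized Cohort Data then calls for a "robust Poisson regression model identical to the model defined on page 17 and 18". The protocol's Statistical Analyses section likewise adjusts for treatment group and the stratifying variables.

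The inputs are recorded. The protocol's Baseline and Intraoperative Data section states that "Baseline variables include: BW, GA, postnatal age, sex, and multiple measures of illness severity related to outcome", and its list goes on to vasopressor therapy, pH, FiO2 and ventilator type. The section on stratification by diagnosis adds that "preoperative diagnosis of the pediatric surgeon will be recorded". Neither document plans to adjust the randomized comparison for the numeric score or its components.

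**The concern.** A two-level version of a score treats all infants on one side of the cut as having the same prognosis. Differences in risk within each half stay in the residual variation, and chance imbalance between arms within each half is left unadjusted. The numeric score is fixed before treatment is assigned, so using it costs patients nothing.

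This matters somewhat more here than in most trials. The protocol expects adequate power to be hard to achieve, notes that both earlier randomized trials stopped short of their targets, and concedes limited power for effects that are clinically important but smaller than the 15-point difference hypothesized. Covariates are also used unevenly: the propensity analysis of the nonrandomized cohort starts from 25 to 50 baseline measures, while the randomized comparison keeps one binary summary of seven.

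**Working it through.** **Inputs from the documents.** Event rates are 80% (drain) and 65% (laparotomy), so RR = 0.65/0.80 = 0.8125. There are 150 infants per arm. The final efficacy boundary is |z| > 2.02, after looks at 75, 150 and 225 infants with boundaries 4.05, 2.86 and 2.34.

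**Inputs assumed.** The formula, its cut-point and its discrimination are not in the documents. AUC was varied from 0.55 to 0.82. The cut was placed at the median and, as the uneven case, at the 70th percentile.

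**Step 1: the plan's own figures.** Exact enumeration of the two-sided Fisher test at 150 per arm gives power 0.803 (plan: 80%). Simulating the four-look robust Poisson analysis with the tabulated boundaries gives 0.825 (plan: 82%). Both reproduce, and neither relies on a numeric score.

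**Step 2: the comparison.** Trials of 300 infants were simulated at RR 0.8125, with 1:1 allocation within the risk stratum. Two robust Poisson models with sandwich standard errors were fitted to the same data, where s is treatment, r the high/low stratum and x the numeric score:

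- present model: log λ = α + βs + γr
- with the score: log λ = α + βs + γr + δx

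Power is the share of trials with |z| > 2.02 for β. Results without center terms, median cut, 3,000 trials per row:

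| AUC | Power, split only | Power, split + score | Variance ratio |
|---|---|---|---|
| 0.55 | 82.6% | 82.6% | 0.999 |
| 0.66 | 81.7% | 82.0% | 0.991 |
| 0.73 | 83.1% | 83.6% | 0.983 |
| 0.78 | 84.9% | 86.0% | 0.977 |
| 0.82 | 85.4% | 86.4% | 0.973 |

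Simulation error is about 0.7 points per cell, though both models see the same data. Further runs gave no gain at AUC 0.56, and 0.6 to 1.7 points with 1 to 4% lower variance at AUC 0.66 to 0.82. With the cut at the 70th percentile, the gain reached about 3.6 points and 8 to 10% lower variance. No scenario showed a material loss. Adding 16 fixed center effects left the variance ratios similar: at AUC 0.75 with the score in place of the split, 0.979 became 0.980 (median cut) and 0.948 became 0.951 (70th-percentile cut).

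**Step 3: in infants.** Variance falls as 1/N, so a ratio v is worth 300 × (1/v − 1) infants:

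- v = 0.999: 0.3
- v = 0.973: 8.3
- v = 0.96: 12.5 (about 4% of 300)
- v = 0.92: 26
- v = 0.90: 33

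**Step 4: the only stratum effect shown in the documents.** SAP Appendix B uses an illustrative 6% relative difference: 0.80 against 0.752 on drain, 0.65 against 0.611 on laparotomy. Averaged over arms, the strata are at 0.725 and 0.6815, with overall mean 0.703. The share of outcome variance explained by the split is 0.25 × 0.0435² / (0.703 × 0.297) = 0.0023. That is close to the AUC 0.55 row, where the gain is nil.

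**Step 5: fitted values.** With event rates near 80%, a linear score on the log scale can push fitted probabilities past 1. At least one fitted value exceeded 1 in 73% of simulated trials at AUC 0.66, and in over 95% at AUC 0.73 or more. Robust Poisson tolerates this. The SAP's Bayesian model, with a Bernoulli likelihood and a log link, does not.

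**The case against.** The strongest reply is that nothing here is an error. Adjusting for the stratification factors is what the protocol specifies, the SAP follows it, and the stated 82% power holds without a numeric score. The gain rests on an AUC the documents do not supply and vanishes if the score is weak. Where the score is strong, the split has already recovered part of the benefit. All of this stands, and it is why the range starts at zero.

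A second reply is that a numeric score may not exist for analysis. The documents describe a formula with continuous inputs, but they do not say that its value is stored or that every input is complete. This also stands: availability is an inference from how the stratum is assigned, and a missing-value rule is needed.

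A third reply is that changing the primary covariates is more than a wording change. The same model supplies the z-statistics for the interim efficacy looks, and the SAP states that the statistician and the coordinating center are unmasked. That is a fair condition on how the change is made. It does not count against the covariate itself, which is set by a formula fixed before randomization and leaves little room for choice.

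A reader might infer a larger benefit, since covariate-standardized estimators can extract more from the same score: about 7, 13 and 22 infants of 300 at AUC 0.65, 0.70 and 0.75 with a median cut. Those figures belong to a different estimator from the SAP's and do not support a linear term in its robust Poisson model.

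**Conclusion.** The point holds as an efficiency improvement of low priority. The primary model uses only the high/low split, although the formula's inputs are recorded at baseline. In the SAP's own model, the numeric score would add 0 to about 1.7 power points (0 to 4% of N) with a median cut, and up to about 3.6 points (8 to 10% lower variance) with a 70th-percentile cut. These figures rest on assumed AUCs of 0.55 to 0.82, assumed cut-points, the planned 80% and 65% event rates, and a score available for essentially all infants.

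A reader might infer that the primary analysis is biased, or that the stated power is wrong. The documents support neither: the split is the randomization factor, adjusting for it is valid, and the power figures reproduce.

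**What to change.** Prespecify the numeric risk score, computed from the formula used at randomization, as a linear term beside treatment, the high/low stratum and center in the primary robust Poisson model. Apply the same model at the interim efficacy looks and the final analysis, so that the monitored and final statistics match. Have the change settled by people without access to results by arm, and state a simple rule for an infant with a missing pH or FiO2. Keep the present model as a sensitivity analysis. Leave the Bayesian log-binomial model on the high/low stratum, because of the fitted probabilities above 1.

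The cost is a SAP revision, one extra covariate, the missing-value rule and a documented masked decision. No new data collection is needed if the recorded inputs are complete. The downside is that the gain is modest and may be nil.
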